8.4.4.2. Exploratory Anhedonia Measures

To complement the SHAPS we include 3 secondary anhedonia measures: the Effort-Expenditure for Rewards Task (EEfRT), the Visual Analogue Scale for Anhedonia (VAS-Anhedonia) and the Temporal Experience of Pleasure Scale (TEPS). These will be compared in subjects receiving CERC-501 and PBO in exploratory analysis.

The **Effort-Expenditure for Rewards Task** (EEfRT; Treadway et al., 2009) is intended to assess the motivation to pursue rewards, one important dimension of reward-related function. It has been validated in a study of 60 individuals who were screened to have anhedonia with the SHAPS (Treadway et al., 2009). The EEfRT was found to be correlated with the Beck Depression Inventory (BDI) anhedonia scale and the Chapman anhedonia scale. The EEfRT task is a multi-trial game in which participants are given an opportunity on each trial to choose between two different task difficulty levels in order to obtain monetary rewards. For all trials, participants make repeated manual button presses

within a short period of time. Each button press raises the level of a virtual "bar" viewed onscreen by the participant. Participants are eligible to win the money allotted for each trial if they raise the bar to the "top" within the prescribed time period. Each trial presents the subject with a choice between two levels of task difficulty, a 'hard task' and an 'easy task.' Successful completion of hard-task trials requires the subject to make 100 button presses, using the non-dominant little finger within 21 seconds, while successful completion of easy-task trials requires the subject to make 30 button presses, using the dominant index finger within 7 seconds. For easy-task trials, subjects are eligible to win the same amount, \$1.00, on each trial if they successfully complete the task. For hardtask choices, subjects are eligible to win higher amounts that vary per trial within a range of \$1.24 - \$4.30 ("reward magnitude"). Subjects are not guaranteed to win the reward if they complete the task; some trials are "win" trials, in which the subject receive the stated reward amount, while others are "no win" trials, in which the subject receives no money for that trial. To help subjects determine which trials are more likely to be win trials, subjects are provided with accurate probability cues at the beginning of each trial. Trials have three levels of probability: "high" 88% probability of being a win trial, "medium" 50% and "low" 12%. Probability levels always apply to both the hard task and easy task, and there are equal proportions of each probability level across the experiment. Each level of probability appears once in conjunction with each level of reward value for the hard task. All subjects receive trials presented in randomized order.

All trials begin with a 1-second fixation cross, following a 5-second choice period in which subjects are presented with information regarding the probability of receiving reward and the reward magnitude of the hard task. Subjects are told that if they did not make a choice within 5 seconds, they will be randomly assigned to either the easy or the hard task for that trial. After making a choice, subjects are then shown a 1-second "Ready" screen and then they complete the task. Following task completion, subjects are shown a 2 second feedback screen informing them that the task was successfully or unsuccessfully completed. If subjects successfully complete the task, then a second feedback screen appears for 2 seconds in which subjects are told whether they had won money for that trial (reward feedback). In total, easy-task trials take approximately 15 seconds, whereas hard-task trials take approximately 30 seconds.

Subjects are told that they will receive a base-rate of compensation for their participation. In addition, they are told that two of their win trials will be randomly selected at the end of the experiment as "incentive trials," for which they will receive the actual amount won on those trials. Subjects are informed that they have twenty minutes to play as many trials as they can. Since hard-task trials take approximately twice as much time to complete as easy-task trials, the number of trials that the subject is able to play depends in part on the choices that he or she makes. This means that making more hard-task trials toward the beginning of the experiment could reduce the total number of trials, which could in turn mean that the subject does not get a chance to play high-value, high-probability trials that might appear towards the end of the playing time. This trade-off is explained clearly to the subject. Importantly, subjects are not provided with any information regarding the distribution of trial types. The goal of this trade-off is to ensure that neither a strategy of always choosing the easy or the hard option could lead to an 'optimal' performance on the task. Moreover, the complexity of variables (with varying monetary reward levels, probability, and loss of time for future trials), does not lend itself to a formal calculation

of an optimal response selection, and subjects are required to make decisions within a brief amount of time. This is done to help ensure that subject decisions reflected individual differences in the willingness to expend effort for a given level of expected reward value.

The VAS-Anhedonia is a standard VAS assessment of anhedonia severity which is included because it provides a global anhedonia indicator which takes very little time to obtain and which was found to be sensitive to change with treatment in a prior placebocontrolled trial in alcohol dependent subjects (Martinotti et al., 2011). The test consists of making a rating on a 100 mm scale in response to the directive: "Make a mark on the line below that indicates how much pleasure you experience from food, sexual behavior, and meeting friends". At the left end of the scale is the anchor "No Pleasure" and at the right end of the scale is the anchor "Extreme Pleasure."

We also include the **Temporal Experience of Pleasure Scale** (TEPS) because it provides different information about reward-related function than the SHAPS and has been found to be correlated with activation in the key circuits of interest (nucleus accumbens and putamen) in Monetary Incentive Delay Task-related fMRI (Stanford et al., 2011). The TEPS is an 18-item self-report measurement of anticipatory (10 items) and consummatory (eight items) components of anhedonia which consists of a series of statements that must be rated according to how accurate they are for the individual (Gard et al., 2006). The scale differentiates the role of anticipatory pleasure ('wanting') from consummatory pleasure ('liking'). Both components are currently believed to be relevant to measuring anhedonia.

8.4.4.3. Other Exploratory Measures

The **Hamilton Rating Scale for Depression** (HAM-D) 17-item version (Hamilton, 1967) will be included in exploratory analysis to provide confirmatory support for changes in depression severity with treatment. This interviewer-administered semi-structured interview is one of the most widely used instruments in depression treatment studies.

The **Hamilton Rating Scale for Anxiety** (HAM-A) is a rating scale designed to measure the severity of anxiety symptoms (Hamilton, 1959). It is widely used in both clinical and research settings. The scale consists of 14 items, each defined by a series of symptoms, and measures both psychic anxiety (mental agitation and psychological distress) and somatic anxiety (physical complaints related to anxiety). It has been demonstrated to acceptable reliability, validity and sensitivity to change (Maier, 1988). Each item is scored on a scale of 0 (not present) to 4 (severe), with a total score range of 0–56, where <17 indicates mild severity, 18–24 mild to moderate severity and 25–30 moderate to severe. This instrument will be included in secondary analysis to provide confirmatory support for changes in anxiety severity with treatment.

The **Cognitive and Physical Functioning Questionnaire** (CPFQ) is a 7-item self-report instrument was intended to be a brief scale for measuring cognitive and executive dysfunction in patients with mood and anxiety disorders (Fava et al., 2009). This scale

has been demonstrated to have strong internal consistency, good temporal stability and sensitivity to change with treatment (Fava et al., 2009).

The **Clinical Global Impression - Severity** (CGI-S) is a widely administered clinician rated global measure of subject overall illness severity. Subjects are rated on a 1-7 scale where 1 corresponds to "Normal, Not at All III", 2 is "Borderline Mentally III", the anchor for 3 is "Mildly III", the anchor for 4 is "Moderately III", 5 is "Markedly III", 6 is "Severely III", and 7 is "Among the Most Extremely III Patients". It will be administered at all subject visits.

The **Clinical Global Impression - Improvement** (CGI-I) is a widely administered clinician rated global measure of the degree of improvement from the initial assessment in subject overall illness severity. Subjects are rated on a 1-7 scale where 1 corresponds to "Very Much Improved", 2 is "Much Improved", the anchor for 3 is "Minimally Improved", the anchor for 4 is "No Change", 5 is "Minimally Worse", 6 is "Much Worse", and 7 is "Very Much Worse". It will be administered at all subject visits.

• During the course of the trial subjects for whom the CGI-I is greater than 5 will be removed from the study and appropriate care given, for safety purposes.

9. STATISTICAL ANALYSIS

9.1. Analysis of Data/Study Outcomes

9.1.1. Analysis of data/ study outcomes

9.1.1.1. Data Management

All data management activities, including establishing a trial electronic case report form and procedures for randomization will be done within the framework of the Duke Clinical Research Institute (DCRI) and will conform to FDA GCP requirements.

Electronic data validation checks with data entry discrepancy flags will utilized. The flags will be triggered by missing values, logically inconsistent values, and values beyond limits. Data checks will be automated and occur daily and lead to the generation of queries in the EDC system which are communicated to the sites. The sites will then review the queries and make appropriate clarifications and corrections. The EDC system will also track queries and produce reports of outstanding queries.

As the sites are entering data, on-screen edit checks run real-time to catch missing values, out of range values, and logical inconsistencies. These will be specified by the DCRI Clinical Data Specialist (CDS) working in conjunction with the statistician. The sites will be trained on reliably entering data. A final database audit on a representative sample of the data will also be carried out.

9.1.1.2. Interim Analysis.

There will be no interim analysis carried out.

9.1.1.3. Primary Outcome Measures

• **Reward-Related Circuit Engagement POC Outcome** for the study will be taskrelated fMRI ventral striatal (e.g., nucleus accumbens) activation occurring with reward and anticipation during the Monetary Incentive Delay (MID) Task

9.1.1.4. Secondary Outcome Measures

- Clinical Anhedonia Outcome for this study will be the total score Snaith-Hamilton Pleasure Scale (SHAPS)
- **Behavioral Anhedonia Outcome** for this study will be Response Bias and Reward Learning Scores on the Probabilistic Reward Task (PRT)

9.1.1.5. Exploratory Outcome Measures

- Ventral striatal fMRI activation during anticipation of loss during the MID Task
- Resting state delta EEG current density in the rostral anterior cingulate
- Resting state fMRI connectivity
- Self-rated affective responses to cues and feedback during the MID Task
- The Effort-Expenditure for Rewards Task (EEfRT)
- The Visual Analogue Scale for Anhedonia (VAS)
- The Temporal Experience of Pleasure Scale (TEPS)
- The Hamilton Depression Rating Scale (HAM-D)
- The Hamilton Anxiety Scale (HAM-A)
- The Cognitive and Physical Functioning Questionnaire (CPFQ)
- Clinical Global Impression Severity (CGI-S)
- Clinical Global Impression Improvement (CGI-I)
- Safety and tolerability of CERC-501 on systematically collected and spontaneously reported adverse events

9.1.2. Planned analyses and statistical methodology to be used

We will employ "Intention-to-Treat" (ITT) principles. Statistical tests will be performed based on a two-sided test at the 5% level of significance. Supporting analyses will also be performed. A "per protocol" analysis will restrict the analysis to participants who receive minimal exposure to the intervention, have a minimal number of longitudinal evaluations, and/or are free of major protocol violations. A "completer" analysis will only include participants who completed acute treatment without exiting or prematurely terminating from their assigned treatment. Because participants may be removed differentially across the treatment arms in these analyses, both approaches are vulnerable to differential selection bias and will be interpreted cautiously.

Most of the study outcomes are observed repeatedly at well-defined time-points postrandomization, so that statistical methods for repeated measures data will be applied. This includes the linear model with structured covariance matrices and the mixed effects models as implemented in PROC MIXED in SAS. Site will also be included as an independent variable in order to account for variability among the study sites.

Covariates in Regression Models: The baseline value of the outcome, centered about its sample mean, will be included in each analysis. Otherwise, only age and sex will be entered as covariates.

Missing Values: We will proactively monitor the amount of missing data, and ensure that we respond quickly to emerging problems. Statistically, missing data will be addressed through the use of mixed models analysis which will be carried out with PROC MIXED in SAS. We will carry out an assessment of the degree to which the structured covariance matrix in mixed effects models fits the data.

Other Confounders Arising Post-Randomization: Logistic regression analysis will be carried out to investigate: (a) adherence to the assigned study intervention (this will include serum levels of study drug and blister pack check data), (b) co-administration of psychotropic medications, and (c) discontinuation from the study intervention. First, we will determine whether these effects occur differentially across the treatment arms suggesting that a differential selection bias may have influenced the results. Then, we will investigate whether baseline characteristics are predictive of any behavior. This will include demographic characteristics, initial severity as measured by the baseline values of the outcome variables, and clinical characteristics such as diagnoses and medications taken at baseline.

Magnitude of the Clinical Effect: To evaluate the clinical significance of the impact of treatment on outcome, effect sizes (Hedge's g) will be calculated as (ME - MC) / SD pooled, where ME represents the adjusted mean of experimental treatment, MC represents the adjusted mean of the comparison treatment, and SD pooled represents pooling of the standard deviations from within both groups. We will also assess how the estimated magnitude of treatment effect and the estimated standard deviation deviate from those postulated in sample size planning.

fMRI Analysis: The monetary incentive delay task entails three key task phases: anticipating making a response, anticipating an outcome, and receiving that outcome. Functional brain responses to these three task phases will be identified using a General Linear Model based statistical analyses (GLM). Here, a statistical test is carried out between the actual data (fMRI time series) and a predicted model (event timings and parametric modulations by behavior). If the fit between the predicted and actual data is good, then a relationship is concluded to exist between the actual data (voxel intensity values) and task-related factors (anticipation, response, receipt). Having tested the fit at the single subject level for each experimental session, the data will be combined into a second-level, random-effects, repeated-measures analysis of variance. Statistical inferences about task effects will be made after appropriate correction for multiple comparisons. Regions of interest or ROIs will be defined with reference to a standard brain atlas (that of Talaraich and Tournoux). The fMRI primary analysis (see below) will focus on the ventral striatum. However, exploratory analyses will be carried out with other ROIs. Cluster-wise parameter estimates for each condition (anticipation, response, receipt) will be extracted for the ventral striatum (and from the other predefined ROIs for exploratory analysis) and correlated with receptor occupancies. In this manner our regression analyses will be robust to non-independence error.

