4.4. Study Procedures

Baseline: Day 0 Visit (6 – 8 hours):

Following rigorous screening, subjects will return to the clinic/research unit up to 30 days later and undergo the following assessments and procedures:

- Structural MRI, fMRI during Monetary Incentive Delay Task, Resting State Connectivity fMRI
- Interval history
- Battery of clinical laboratory tests including: Complete blood count with differential, Electrolytes, Metabolic Panel, Thyroid Function Tests, Urinalysis.
- EEG
- Vital signs (temperature, blood pressure, and pulse)
- Physical examination
- Electrocardiogram (ECG)
- Snaith-Hamilton Pleasure Scale (SHAPS)
- Temporal Experience of Pleasure Scale (TEPS)
- Visual Analogue Scale for Anhedonia (VAS)
- Columbia Suicide Severity Rating Scale (CSSRS)
- Probabilistic Rewards Task (PRT)
- Effort Expenditure for Rewards Task (EEfRT)
- Hamilton Depression Rating Scale (HAM-D)
- Hamilton Anxiety Rating Scale (HAM-A)
- The Cognitive and Physical Functioning Questionnaire (CPFQ)
- Clinical Global Impression Severity (CGI-S)
- Clinical Global Impression Improvement (CGI-I)
- Adverse events assessment with the Patient Reported Inventory of Side-Effects (PRISE)
- Blood sample collection for tests for assessment for gastric adverse events including gastrin, and pepsinogen I/II levels.
- Blood sample collection to be sent to Rutgers for potential genetic analysis or other future analysis (optional)

At the end of this visit subjects will be randomized to CERC-501 10 mg or placebo, will be provided with enough study medication for a 2-week period and will be instructed to take the medication every morning. Subjects will also be instructed to bring all of their study drug packaging and unused study drug with them to each visit.

Week 1 – Telephone Follow Up:

Subjects will be called after one week to assess for any safety concerns. Any safety issues identified will be addressed as appropriate.

Week 2 Visits (4 – 6 hours per visit): +/- 4 days

At this visit subjects will undergo the following assessments and procedures:

- Interval history
- Battery of clinical laboratory tests including: Complete blood count with differential, Electrolytes, Metabolic Panel, Thyroid Function Tests, Urinalysis
- Vital signs (temperature, blood pressure, and pulse)
- Physical examination
- Electrocardiogram (ECG)
- Snaith-Hamilton Pleasure Scale (SHAPS)
- Temporal Experience of Pleasure Scale (TEPS)
- Visual Analogue Scale for Anhedonia (VAS)

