The SHAPS covers four domains of hedonic experience: interest/pastimes, social interaction, sensory experience, and food/drink (Snaith et al., 1995). Participants completing the SHAPS are instructed to respond based on their ability to experience pleasure "in the last few days." This scale has shown adequate overall psychometric properties in clinical and student samples (Gilbert el al., 2002; Snaith et al., 1995). The SHAPS convergent validity has been supported by its correlations with MADRS Hedonic Tone item, the Mood and Anxiety Symptom Questionnaire Anhedonic Depression subscale, and Positive and Negative Affect Schedule-Positive Affect subscale (Gilbert et al., 2002; Snaith et al., 1995). Its discriminant validity has been supported by its lack of association with MADRS Depressed Mood and Anxiety items (Snaith et al., 1995). The SHAPS has satisfactory test-retest validity in healthy participants over an interval of three weeks (intraclass correlation coefficient between test and retest: r = .70, p < .001; Franken et al., 2007). Besides being well-validated, the SHAPS is of utility for our study because there is an established cutoff for clinical significance. Although this is also true for the Anhedonic Depression subscale of the Mood and Anxiety Symptoms Questionnaire (MASQ), we wanted a scale that assessed anhedonia and was not depression specific or specific to any other disorder given the goal of using it across diagnostic boundaries. ROC using the MADRS anhedonia item score (cutoff was clinically significant level) as a discriminator suggests that a SHAPS score of ≥ 20 corresponds to clinically significant anhedonia (Snaith et al., 1995). This was validated in 30 volunteers from the general population. It should be noted that the original ROC analysis was done with dichotomous ratings rather than the current 4 option rating system. The original finding was that 3 or more negative answers indicated clinical significance which corresponds to a score of at least 20 with the current rating system.

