9.1.2.3. Exploratory Analysis

Exploratory mixed effects model analyses will also be carried out with the exploratory outcomes of the study. This includes: ventral striatal fMRI activation during anticipation of loss during the MID Task; resting state delta EEG current density in the rostral anterior cingulate; resting state fMRI connectivity; self-rated affective responses to cues and feedback during the MID Task; EEfRT total reward; VAS score; TEPS anticipatory and consummatory pleasure scores; HAM-D score; HAM-A score; CGI-S, CGI-I, and CPFQ score.

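### The covariate rule gives the CGI-I model a Day 0 change rating as its baseline and leaves out baseline CGI-S, the severity rating from the same visit

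*Protocol*

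**What the plan says.** Protocol Section 9.1.2, under covariates, sets one rule for all outcomes: "The baseline value of the outcome, centered about its sample mean, will be included in each analysis". It then limits what else may enter: "Otherwise, only age and sex will be entered as covariates". The same section adds site: "Site will also be included as an independent variable in order to account for variability among the study sites". No outcome is exempted.

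Section 9.1.2.3 lists the exploratory outcomes to be modelled, among them "HAM-D score; HAM-A score; CGI-S, CGI-I, and CPFQ score". Section 8.4.4.3 describes CGI-I as a "clinician rated global measure of the degree of improvement from the initial assessment in subject overall illness severity", scored 1 to 7 with 4 meaning no change. Both CGI-I and CGI-S are rated at the Day 0 visit, before treatment (Section 4.4 and Table 3).

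The Protocol is not consistent about CGI-I at screening. The study overview (Section 4.1) lists it there, and Section 8.4.4.3 says it is given at all visits. The screening list in Section 4.3 and the screening column of Table 3 show CGI-S but not CGI-I.

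The SAP text we have covers objectives and background and gives no covariate specification. Part of the SAP is not in that text, so a rule elsewhere in it cannot be excluded.

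**The concern.** Adjusting for an outcome's own baseline works because the baseline measures the same thing before treatment and so predicts the later value. CGI-I does not fit that pattern. It is already a comparison with an earlier visit, so its Day 0 score says nothing direct about how ill the subject is at entry. The matching severity score, CGI-S, is taken at the same visit, but the closed list keeps it out of the CGI-I model.

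What is at stake is the width of the confidence interval for the CGI-I treatment effect. There is also a practical problem: the analyst cannot apply the rule sensibly without knowing which visit the Day 0 CGI-I is compared with, and the Protocol does not settle that.

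**Working it through.** **1. The plan's own precision figure.** Section 9.2 gives a detectable effect of 0.58 with 72 subjects (36 per arm), one-tailed alpha 0.05 and 80% power. Check: (1.645 + 0.842) × √(2/36) = 0.586, and power at 0.58 is 79.3%. The figure reproduces. It is an unadjusted calculation for the fMRI primary, so the covariate rule does not enter it. The plan gives no precision figure for CGI-I.

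**2. What the rule delivers for CGI-I.**

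- *Reference visit is Day 0.* Every Day 0 score should be 4. Centred about its mean, the covariate is 4 − 4 = 0 for everyone and removes 0% of variance. The model then has no adjustment for initial clinical state.
- *Reference visit is screening.* Day 0 CGI-I records change over a gap of up to 30 days, during which some subjects taper medication (Sections 4.1 and 4.3). It may vary and may predict outcome, but it is still not severity.

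**3. Size when Day 0 CGI-I is constant.** Let r be the correlation of baseline CGI-S with Week 8 CGI-I, given site, age and sex. The documents give no value, so 0.1 to 0.4 is assumed. Residual variance is multiplied by 1 − r². The detectable standardised difference, two-sided 0.05 (Section 9.1.2) with 36 per arm, is (1.960 + 0.842) × √(2/36 × (1 − r²)).

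CGI-S also uses one parameter that a zero covariate does not. In a single-visit linear model with treatment, five site terms, age and sex, adding one covariate inflates the expected variance by (n − 10)/(n − 11), which is 62/61 = 1.016 at n = 72. The net column is (1 − r²) × 62/61.

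| r | 1 − r² | Variance removed | Detectable difference (before the parameter charge) | Net variance ratio, n = 72 |
|---|---|---|---|---|
| 0 | 1.00 | 0% | 0.660 | 1.016 |
| 0.1 | 0.99 | 1% | 0.657 | 1.006 |
| 0.2 | 0.96 | 4% | 0.647 | 0.976 |
| 0.3 | 0.91 | 9% | 0.630 | 0.925 |
| 0.4 | 0.84 | 16% | 0.605 | 0.854 |

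Break-even at n = 72 is r² = 1/62 = 0.016, or r of about 0.13.

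**4. Size when Day 0 CGI-I varies.** If it correlates r_I with Week 8 CGI-I, swapping it for CGI-S multiplies residual variance by (1 − r²)/(1 − r_I²). With both at 0.3 this is 0.91/0.91 = 1, so the swap gains nothing. If r_I exceeds r, the swap loses. In this case CGI-S is better added than substituted.

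**The case against.** CGI-I is one of many exploratory outcomes and no decision rests on it. A covariate that is zero for everyone does no harm. If Day 0 CGI-I does vary, it may be prognostic, and replacing it outright could discard information. A short, closed, pre-specified covariate list is a proper safeguard against choosing covariates after seeing results. Every correlation used above is assumed, and the SAP may say something different.

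All of this stands as a limit on the size of the point. It does not make the rule fit CGI-I. A harmless covariate still leaves the model without the severity adjustment that the rule is evidently meant to supply. Pre-specification is a reason to correct the wording in advance, because adding CGI-S after unblinding would depart from a list that says only.

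A reader might also infer that the closed list wastes precision on SHAPS, a secondary outcome, because SHAPS is scored at both screening and Day 0 and only the Day 0 score is used. The documents do not support that as a defect. The SHAPS model already carries its own baseline. Take the screening-to-baseline correlation as 0.70 (Section 8.4.2, healthy participants over three weeks) and assume a baseline-to-Week 8 correlation of 0.5. Adding a screening score with Week 8 correlation r_s gives R² = (0.25 + r_s² − 0.7 r_s)/0.51, against 0.25 for baseline alone. Residual variance falls by 0% at r_s = 0.35, 1.5% at 0.425 and 5.9% at 0.50. The extra parameter costs (n − 11)/(n − 12): 61/60, or 1.7%, at n = 72 and 79/78, or 1.3%, at n = 90. The net result is a loss of 1.3% to 1.7%, roughly break-even, and a gain of 4.3% to 4.7%. The gain needs an older score, possibly taken before washout and with its range cut by the entry threshold of 20, to predict as well as the newer one. Whether to include it is a matter of preference.

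**Conclusion.** The point holds for CGI-I and is minor. As written, Section 9.1.2 gives the CGI-I model either an empty covariate or a pre-treatment change score, and it excludes baseline CGI-S.

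The loss is about 1% to 16% of residual variance under assumed correlations of 0.1 to 0.4 with Day 0 CGI-I constant. After the parameter charge at n = 72, this runs from essentially nothing to just under 15%. It is smaller if Day 0 CGI-I varies and carries information. The 72 is the plan's worst case for complete data and counts scan losses, so more subjects may contribute to CGI-I and the charge would then be slightly lower.

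A reader might infer that the CGI-I comparison is biased or that the trial's main result is weakened. Neither follows. Randomisation keeps the treatment estimate valid with an uninformative covariate, and the fMRI primary does not use CGI-I.

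**What to change.** In Section 9.1.2, and in the SAP if it carries its own covariate rule, state before unblinding that the CGI-I model uses baseline CGI-S as its baseline covariate. If CGI-I is referenced to screening and its Day 0 scores vary, the Day 0 CGI-I may be kept alongside CGI-S.

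Reconcile Sections 4.1 and 8.4.4.3 with Section 4.3 and Table 3 on whether CGI-I is rated at screening, and name its reference visit. The same rating feeds the individual stopping criterion in Section 7.2, so the clinical team should settle that point; no clinical rule is proposed here.

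The cost is a sentence or two of wording and at most one or two degrees of freedom in one exploratory model. No new data are needed. The SHAPS model can stay as it is.
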